## **Prior/Concomitant Therapy**

- 9. Has had chemotherapy, definitive radiation, or biological cancer therapy within 4 weeks (2 weeks for palliative radiation) prior to the first dose of study therapy, or has not recovered to baseline or CTCAE Grade 1 (Grade 2 alopecia is allowed) from the AEs due to cancer therapeutics administered more than 4 weeks earlier.
- 10. Is currently participating and receiving study therapy or has participated in a study of an investigational agent and has received study therapy or has used an investigational device within 28 days of administration of MK-2118.

**Note:** Prior exposure to MK-2118 is allowed, provided the participant has a washout period of at least 14 days and did not experience ≥ Grade 3 drug-related toxicity.

**Note:** Prior exposure to immunotherapeutics is allowed, including PD-1 and PD-L1 inhibitors, provided participant did not experience a  $\geq$  Grade 3 drug-related toxicity on monotherapy with a PD-1 or PD-L1 inhibitor

**Protocol/Amendment No.:** 001-08

11. Is expected to require any other form of antineoplastic therapy while on study.

12. Is on chronic systemic steroid therapy in excess of replacement doses (prednisone  $\leq 10 \text{ mg/day}$  is acceptable), or on any other form of immunosuppressive medication.

Note: The use of physiologic replacement doses of corticosteroids may be approved after consultation with the Sponsor Medical Monitor.

- 13. Has been treated within 2 weeks of Cycle 1 Day1 with any of the following:
  - strong/moderate CYP2C9 inhibitors, such as: amiodarone, felbamate, fluconazole, miconazole, piperine, oxandrolone, fluorouracil and its derivatives (TS-1, UFT, tegafur, carmofur, doxifluridine, capecitabine), sulfaphenazole, cyclosporine, bucurol, tienilic acid.
  - UGT1A3 inhibitors, which include ritonavir, quinidine, probenecid, and valproic acid
  - strong CBR inhibitors, which include quercetin, menadione, glycyrrhetinic acid, and flufenamic acid.
- 14. Has received a live vaccine within 28 days prior to first dose.
- 15. Has been treated with a STING agonist other than MK-2118 in Arm 1 (eg, MK-1454, ADU-S100).
- 16. Has a history of re-irradiation for HNSCC at the projected injection site.

## **6.3** Lifestyle Restrictions

#### **6.3.1** Meals and Dietary Restrictions

Participants should maintain a normal diet unless modifications are required to manage AEs such as diarrhea, nausea, or vomiting.

#### 6.3.2 Caffeine, Alcohol, and Tobacco

There are no restrictions on caffeine.

During each dosing session, participants will abstain from alcohol for 24 hours before the start of dosing until after collection of the final PK and/or pharmacodynamic sample.

Participants who use tobacco products will be instructed that use of nicotine-containing products (including nicotine patches) will not be permitted while they are in the clinical unit.

**Protocol/Amendment No.:** 001-08

# 6.3.3 Activity

Sunscreen should be applied daily to exposed skin areas regardless of season. Participants should be encouraged to stay out of the sun. Protective clothing for sun protection and wearing a hat is recommended.

#### 6.3.4 Contraception

Pembrolizumab may have adverse effects on a fetus in utero. Furthermore, it is not known if pembrolizumab has transient adverse effects on the composition of sperm.

MK-2118 should not be used by pregnant women.

Participants should be informed that taking the trial medication may involve unknown risks to the fetus (unborn baby) if pregnancy were to occur during the trial. In order to participate in the trial, women of childbearing potential must adhere to the contraception requirement from the day of trial medication initiation (or 14 days prior to the initiation of trial medication for oral contraception) throughout the trial period up to 120 days after the last dose of trial medication. If there is any question that a woman of childbearing potential will not reliably comply with the requirements for contraception, that participant should not be entered into the trial.

Definitions of WOCBP and standards for adequate contraception are outlined in Appendix 5.

## 6.3.5 Pregnancy

If a participant inadvertently becomes pregnant while on treatment with pembrolizumab or MK-2118, the participant will be immediately discontinued from trial treatment. The site will contact the participant at least monthly and document the participant's status until the pregnancy has been completed or terminated. The outcome of the pregnancy will be reported to the Sponsor without delay and within 24 hours if the outcome is an SAE (eg, death, abortion, congenital anomaly, or other disabling or life-threatening complication to the mother or newborn). The trial investigator will make every effort to obtain permission to follow the outcome of the pregnancy and report the condition of the fetus or newborn to the Sponsor. If a male participant impregnates his female partner, the trial personnel at the site must be informed immediately and the pregnancy must be reported to the Sponsor and followed as described in Section 9.3.6.

## 6.3.6 Use in Nursing Women

It is unknown whether pembrolizumab or MK-2118 is excreted in human milk. Because many drugs are excreted in human milk, and because of the potential for serious adverse reactions in the nursing infant, participants who are breastfeeding are not eligible for enrollment.

**Protocol/Amendment No.:** 001-08

#### 6.4 Screen Failures

Screen failures are defined as participants who consent to participate in the clinical study but are not subsequently entered in the study. A minimal set of screen failure information is required to ensure transparent reporting of screen failure participants to meet the Consolidated Standards of Reporting Trials (CONSORT) publishing requirements and to respond to queries from regulatory authorities. Minimal information includes demography, screen failure details, eligibility criteria, and any AEs or SAEs meeting reporting requirements as outlined in the entry guidelines.

# 6.5 Participant Replacement Strategy

Participants in Arms 1, 2, and 3 discontinuing within 21 days of the first dose due to reasons unrelated to study treatment will not be considered evaluable for DLTs and may be replaced. Participants in Arm 4 discontinuing within 35 days of the first dose due to reasons unrelated to study treatment will also not be considered evaluable for DLTs and may be replaced. Participants with a DLT within the DLT period should not be replaced. See Section 10.5.1 for description of safety analysis population.

#### 7 TREATMENTS

Study treatment is defined as any investigational treatment(s), marketed product(s), placebo, or medical device(s) intended to be administered to a study participant according to the study protocol.

Clinical supplies [study treatment(s) provided by the Sponsor] will be packaged to support enrollment and replacement participants as required. When a replacement participant is required, the Sponsor or designee needs to be contacted prior to dosing the replacement supplies. Clinical supplies will be affixed with a clinical label in accordance with regulatory requirements.

#### 7.1 Treatments Administered

The study treatments to be used in this trial are outlined below in Table 7.

**Protocol/Amendment No.:** 001-08

Table 7 Study Treatment(s)

Study Treatment Name:	MK-2118 a	Pembrolizumab, (MK-3475) Arms 2, 3, and 4	MK-2118 Diluent		
Dosage Formulation:	Solution for injection	Solution for infusion	Solution for dosage preparation		
Unit Dose Strength(s):	CCI	100 mg/4 mL	CCI		
Dosage Level(s):	-	200 mg			
Route of Administration:	IT injection or SC injection	IV infusion	IT injection or SC injection		
Sourcing:  Provided centrally by the Sponsor  Provided centrally by the Sponsor or locally by the stu site, subsidiary, or designee					
Abbreviations: IT = intratumoral; IV = intravenous; SC = subcutaneous.  a In Arm 2, 3, and 4, MK-2118 will be administered within following completion of pembrolizumab IV infusion. b Dose levels will be determined based on emerging safety data.					

All supplies indicated in Table 7 will be provided per the 'Sourcing' row depending upon local country operational requirements. Every attempt should be made to source these supplies from a single lot/batch number. The trial site is responsible for recording the lot number, manufacturer, and expiry date for any locally purchased product as per local guidelines unless otherwise instructed by the Sponsor.

Refer to section 9.1.8 for details regarding administration of the study treatment.

## 7.1.1 IT Injection (Arm 1, Arm 2, and Arm 3)

In Arms 1 and 2, MK-2118 will be administered by IT injection into cutaneous, subcutaneous, and/or nodal lesions that are visible, palpable, or detectable by ultrasound guidance.

In Arm 3, MK-2118 will be administered by injection into liver metastasis/lesions by ultrasound or cross-sectional imaging guidance (CT/MRI).

During dose escalation in both Arm 1 and Arm 2, each participant at a given dose level will receive a fixed dose of MK-2118 diluted in a volume of of diluent. See Table 2 and Table 3 for dose level ranges within Arm 1 and Arm 2, respectively. The volume of injectate delivered to each lesion will be based on the longest dimension of the target lesion as shown in Table 8, and on the number of lesions injected [Rehman, H., et al 2016]. Documentation of dose volume administered per lesion will be obtained.

**Protocol/Amendment No.:** 001-08

During dose escalation in Arm 3, each participant at a given dose level will receive a fixed dose of MK-2118 diluted in a volume of of diluent. See Table 4 for dose level ranges within Arm 3. The volume of injectate delivered to each lesion will be based on the longest dimension of the target lesion as shown in Table 9, and on the number of lesions injected.

Regarding prioritization of lesions to be injected at a treatment visit, any new or progressing lesion should be injected first, followed by injection of the largest lesion, with up to a total volume of injectate of 4 mL per treatment visit. Injection of more than one lesion, if feasible, is suggested. See Appendix 7 for further guidance.

For Arms 1 and 2, if there are multiple lesions, then up to a maximum of 8 lesions may be injected per treatment visit, with a minimum injectate volume of 0.5 mL per lesion, and a total injectate volume of 4 mL per treatment visit.

For Arm 3, if there are multiple lesions, then up to a maximum of 4 lesions may be injected per treatment visit, with a minimum injectate volume of 1 mL per lesion, and a total injectate volume of 4 mL per treatment visit.

For lesions that are no longer visible following treatment, discuss with Sponsor for continued injection. Distant lesion(s) assessed for "abscopal" response should not be injected, unless approved by the Sponsor Medical Monitor or designee. Deviation from the injectate volumes specified in Table 8 and in Table 9 for individual lesions may be permitted upon approval by the Sponsor Medical Monitor or designee under selected scenarios; eg, allocating the total injectate volume among multiple lesions rather than delivering the entire volume to the largest lesion.

Details on dose calculation, preparation, and administration of MK-2118 are provided in the Procedures Manual.

Table 8 Determination of MK-2118 Injection Volume for Cutaneous and Subcutaneous Injections Based on Lesion Size (Arms 1 and 2)

Lesion Size (longest dimension)	Injection Volume
>5.0 cm	≤ 4 mL
>2.5 cm to 5.0 cm	≤ 2 mL
>1.5 cm to 2.5 cm	≤ 1 mL
≥1.0 cm to 1.5 cm a	0.5 mL

<sup>a Doses CCl require a minimum of 1 mL of total injectate volume.

**Protocol/Amendment No.:** 001-08

Table 9 Determination of MK-2118 Injection Volume for IT Injections Based on Visceral Lesion Size (Arm 3)

Lesion Size (longest dimension)	Injection Volume
>5.0 cm	≤ 4 mL
>2.5 cm to 5.0 cm	≤ 2 mL
>1.5 cm to 2.5 cm	≤ 1.5 mL
≥1.0 cm to 1.5 cm a	1.0 mL

<sup>a Doses of total injectate volume.

# 7.1.2 Subcutaneous Injection (Arm 4)

for dosing SC MK-2118. Sites will determine the appropriate volume of subcutaneous injection based on the dose to be administered at each dose cohort. The Procedures Manual provides a guide to injection volume calculation for subcutaneous administration by dose. Note that lesion size does not impact the volume administered of MK-2118 in Arm 4. Administration will be via injection into the subcutaneous anterolateral abdominal tissue or into the subcutaneous anterolateral thigh tissue. Subcutaneous administration of MK-2118 is by the Investigator or qualified designee.

Dose escalation of subcutaneous MK-2118 beyond the projected upper dose limit may be allowed if the systemic exposure achieved by SC dosing is significantly lower than expected, or if the subcutaneous dosing of MK-2118 at the upper dose limit demonstrates sufficient safety and tolerability in humans.

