For Arm 4, the study will enroll participants with advanced solid tumors or lymphomas with at least 1 measurable, discrete lesion that is amenable to biopsy. MK-2118 will be administered by subcutaneous injection in Arm 4. There is no IT injection of MK-2118 in Arm 4. This discrete lesion will undergo biopsy prior to MK-2118 SC administration during Screening, as well as on Cycle 1 Day 8, and on Cycle 3 Day 8, unless deemed medically unsafe by the Investigator. Arm 4 will initiate once dose escalation in Arm 1 has proceeded beyond the col MK-2118 dose level. Once initiated, Arm 4 will dose escalate independently of Arms 1, 2 and 3.

27-Sep-2022 Confidential

**Protocol/Amendment No.:** 001-08

In Arms 1, 2, and 3, all participants will undergo at least a 24-hour inpatient observation period following dose administration on C1D1, C1D8, and C1D15. In Arm 4, a 24-hour inpatient observation period will follow MK-2118 administration on C1D1, C1D8, and C2D1. These inpatient observation periods may be extended to 48 hours at the discretion of the Investigator, per local Institutional Review Board, Ethics Review Committee, and/or Health Authority mandate. After discharge from the clinic, participants are to be counseled with post-discharge instructions.

In all 4 Arms, dose escalation of MK-2118 will proceed based on emerging safety and tolerability data. Each participant will be monitored for DLTs over the DLT evaluation period (21 days from initiation of study drug in Cycle 1 for Arm 1, Arm 2, and Arm 3; 35 days from initiation of study drug in Cycle 1 for Arm 4). For each dose level, an assessment will be made of the safety and tolerability data prior to escalating to the next dose level. The trial will proceed in an ATD up to a dose that meets at least 1 of the following criteria: 1) a dose level of at least  $^{\text{CCI}}$  is cleared by DLT evaluation OR 2) a  $\geq$  Grade 2 toxicity as assessed by the Investigator to be related, probably related, or possibly related to the drug(s) at any dose level.

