Dose escalation of MK-2118 to determine the MTD/MAD will be guided by the mTPI design, targeting a DLT rate of 30%, with a tolerance interval of 3%. Doses of MK-2118 for IT administration used in combination with pembrolizumab will not exceed the MTD for monotherapy. If an MTD for the monotherapy arm is established, then the dose of IT MK-2118 in combination may continue escalation up to that established dose. For example, if the MTD for monotherapy (Arm 1 Part A) is MK-2118, then the starting dose for combination therapy (Arm 2 Part C), if no DLTs occurred in monotherapy, would be MK-2118, with a maximum dose escalation to MK-2118. If the MTD for monotherapy (Arm 1, Part A) is MK-2118, then the starting dose for combination

**Protocol/Amendment No.:** 001-08

therapy will be MK-2118. If in monotherapy (Arm 1, Part A), the dose level of MK-2118 is completed and no DLTs occurred in monotherapy, then the starting dose in combination therapy (Arm 2 Part C) could be MK-2118 (assuming sequential monotherapy dose cohorts of MK-2118).

Dose escalation of SC MK-2118 in Arm 4 will be guided by clinical safety and tolerability. The dose of SC MK-2118 may be higher than the MAD achieved in IT MK-2118 administration in Arms 1, 2 and/or 3.

Participants may continue on their assigned treatment for up to 35 cycles for Arm 1, 2, and 3, and up to 36 cycles for Arm 4 (approximately 2 years) from the start of treatment. Treatment may continue until 1 of the following occurs: disease progression, unacceptable AEs, intercurrent illness that prevents further administration of treatment, Investigator decision to withdraw the participant, participant withdraws consent, pregnancy of the participant, noncompliance with trials treatment or procedure requirements, or administrative reasons requiring cessation of treatment.

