a Arm 1 dose escalation will initiate in ATD (Part A) up to a dose that meets at least 1 of the following triggering criteria for a participant at any time during the first treatment cycle of MK-2118: (1) a dose level of at least MK-2118 is cleared by DLT evaluation OR (2) a ≥ Grade 2 toxicity as assessed by the Investigator to be related, probably related, or possibly related to the drug(s) at any dose level. Dose escalation will then proceed to mTPI (Arm 1 Part B).

<sup>b Dose levels will be determined based on emerging safety data.

**Protocol/Amendment No.:** 001-08

Table 3 Trial Treatment for IT MK-2118 Combination Therapy with Pembrolizumab (Arm 2)

Drug	Dose/ Potency	Dose Frequency	Route of Administration	Regimen/ Treatment Period a	Use
Pembrolizumab	200 mg	Q3W	IV infusion	Day 1 of each 21-day cycle	Experimental
MK-2118 b	Range:	for subsequent 21 day cycles	IT via visual inspection for cutaneous lesions, and via ultrasound guidance for subcutaneous lesions, as needed	CCI	Experimental

Abbreviations: ATD = accelerated titration design; DLT = dose-limiting toxicity; IT = intratumoral; mTPI = modified toxicity probability interval;

This conservative approach is being taken to ensure an acceptable safety profile, while continued participant safety will be ensured through appropriate dose escalation design and monitoring in the clinic.

Dose escalation decisions will be made upon ongoing review of safety and PK/PD data at the current dose level. Weekly safety teleconferences will be held with the investigators from all sites. At these weekly safety teleconferences, safety data and PK/PD data will be reviewed for the current dose level, and dose escalation decisions will be made upon a consensus assessment. Subsequent dose levels will be communicated to all sites at the weekly safety teleconferences, and through written correspondence subsequent to the weekly safety teleconferences. Dose level escalations are sponsor-controlled through IWRS, which include the opening and closing of dose level cohorts upon dose escalation.

The injectate volume for Arm 1 and Arm 2 will be determined based on tumor size and number of lesions injected (see Section 7.1.1).

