# 5.5.2.1 Maximum Dose Exposure for IT Dosing

For IT dosing (Arms 1, 2, and 3), the proposed maximum dose/exposure for the trial is a dose of or an exposure limit of whichever is lower.

The rationale for the upper dose limit and exposure limit was initially based on the maximum dose studied in dogs and the exposure level observed at that dose, respectively. The therapeutic dose was initially expected to be less than participants have been treated with doses of up to with no DLTs and have tolerated treatment well. Therefore, the maximum dose of MK-2118 for IT dosing is now This is based on the maximum dose/exposure for subcutaneous dosing (see Section 5.5.2.2), projected from systemic exposure attained in the GLP toxicology study and using standard approaches to scaling in vitro and in vivo preclinical disposition and pharmacology data. No remarkable differences in PK results are expected with IT versus subcutaneous administration.

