# 5.5.2.2 Maximum Dose/Exposure for Subcutaneous Dosing

Arm 4 SC MK-2118 dose escalation is ongoing. Protocol amendment MK-2118-001-06 allows for a maximum SC MK-2118 dose of in Arm 4. This maximum dose for Arm 4 has been increased from the previously proposed maximum SC MK-2118 dose of The elevation of this maximum SC MK-2118 dose in Arm 4 is based on composite evaluation of clinical safety, preclinical safety, PK, pharmacodynamics, and early efficacy analysis. The highest nonseverely toxic dose studied in dogs in the GLP toxicology study was at an exposure of MK-2118 exposure-pharmacodynamic and efficacy relationships were established in tumor-bearing mice and exposure levels were extrapolated to humans. A cumulative plasma exposure range of was predicted to be efficacious. To consistently achieve efficacious exposures within this exposure range in patients, it is predicted that doses up to SC MK-2118 may be required.

Emerging pharmacokinetic data in subjects from Arm 4 SC MK-2118 demonstrate a mean exposure of at a SC MK-2118 dose. To date, available data does not show clinically meaningful changes in explo harmacodynamic biomarkers for SC MK-2118. Dose escalation for SC MK-2118 to date demonstrates an acceptable safety profile. Rigorous safety monitoring will continue, including 24-hour inpatient safety monitoring for the first 3 injections. SC MK-2118 dose escalation will continue per mTPI design to determine the SC MK-2118 RP2D. Continued development of SC MK-2118 is supported by emerging clinical data.

**Protocol/Amendment No.:** 001-08

Dose escalation of SC MK-2118 beyond the projected upper dose limit may be allowed if the systemic exposure achieved by SC dosing is significantly lower than expected and SC dosing of MK-2118 at the upper dose limit demonstrates sufficient safety and tolerability in patients.

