A "D" or "DU" decision at the starting dose level of Arm 1 of the study will stop the trial. An E decision at the highest dose level will result in staying at that level. During dose finding, it may be acceptable to de-escalate to an intermediate dose that was not predefined and not previously studied if evaluation of toxicity at such a dose is desired. If this approach is taken, 3 to 6 new participants may be enrolled at the new intermediate dose, and the aforementioned rules should be used to determine further enrollment at this dose level.

After 14 participants have been enrolled at any of the tested doses (including intermediate doses), dose finding will stop if the mTPI table indicates "S" for staying at current dose. Otherwise, up to 14 new participants may be enrolled at a lower dose if "D" or "DU" is indicated, or at a higher dose if "E" is indicated.

The pool-adjacent-violators-algorithm [Ji, Y., et al 2007] will be used to estimate the DLT rates across doses. The dose with an estimated DLT rate closest to 30% will be treated as a preliminary MTD. However, the totality of the data will be considered before deciding on the dose(s) to carry forward to Phase 2, and the escalation schedule may be adjusted based on pharmacodynamic, PK, and safety data emerging throughout the trial. The preliminary RP2D of MK-2118 in the combination arm (Arm 2) will not exceed, but may equal, the preliminary RP2D in the MK-2118 monotherapy arm (Arm 1).

Note that although 30% was the target toxicity rate used to generate the guidelines in Table 10, the observed rates of participants with DLTs at the MTD may be slightly above or below 30%. The target DLT rate will be 30% with a tolerance interval of 3%.

Establishment of the MTD/MAD for the combination of IT MK-2118 with pembrolizumab (Arm 2) requires that at least half of the participants in that cohort have no prior exposure to MK-2118 (ie, noncrossover participants). Priority for enrollment in Arm 2 will be given to MK-2118-naïve participants. Enrollment into Arm 2 will be monitored through IWRS.

Once the triggering criterion is met in the ATD phase, Arm 3 will use the same dose escalation and confirmation rules as in the mTPI method with a minimum of 3 participants per dose level. Enrollment to Arm 3 will be monitored through IWRS.

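### Section 7.1.2 lets Arm 4 subcutaneous dosing pass its upper dose limit on low exposure or tolerability, where Section 5.5.2.2 requires both

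*Combined protocol and SAP*

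**What the plan says.** Two sections of the current protocol state when Arm 4 may go above the projected upper dose limit.

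- Section 5.5.2.2 allows it if the systemic exposure achieved is "significantly lower than expected and SC dosing of MK-2118 at the upper dose limit demonstrates sufficient safety and tolerability in patients".
- Section 7.1.2 allows it if that exposure is "significantly lower than expected, or if the subcutaneous dosing of MK-2118 at the upper dose limit demonstrates sufficient safety and tolerability in humans".

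Section 7.2.2, whose escalation rules also apply to Arm 4, adds: "An E decision at the highest dose level will result in staying at that level". It mentions no exception for Arm 4.

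The controls around these rules are general ones. Section 5.1 says that for each dose level "an assessment will be made of the safety and tolerability data prior to escalating to the next dose level". Section 5.5.1 says that "dose escalation decisions will be made upon a consensus assessment", after review of safety and PK/PD data, and that "Dose level escalations are sponsor-controlled through IWRS". Section 5.1 also says of Arm 4: "The dose of SC MK-2118 may be higher than the MAD achieved in IT MK-2118 administration in Arms 1, 2 and/or 3".

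On a separate matter, Sections 5.1 and 7.2.1 both allow up to 3 participants in an accelerated-titration (ATD) cohort. Section 5.1 makes this conditional on at least 7 days between the first doses of each of the first 3. Section 7.2.1 states the 7 days for the first 2 and says nothing about a third.

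**The concern.** The two Arm 4 statements give one permission under different logical conditions, and neither refers to the other. Under 5.5.2.2 the limit can be passed only when exposure has fallen short of prediction, so that a higher dose is needed to reach the exposure that was planned for. Under 7.1.2 a well-tolerated limit dose is enough, even when exposure is already where it was expected to be. A further increase would then take participants above the exposure on which the limit was set.

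This is a first-in-human trial, and Section 5.5.2.2 bases the subcutaneous maximum partly on exposure: the dog GLP toxicology exposure and a predicted efficacious range. The word *or* in 7.1.2 removes exposure as a necessary condition for passing that maximum. No section says which wording governs.

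**Working it through.** **The upper-limit rule.** No planned figure is at issue and the dose and exposure values are redacted, so the check is a comparison of the two rules over every combination of their conditions.

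| Exposure well below expected | Limit dose tolerated | 5.5.2.2 (both needed) | 7.1.2 (either suffices) |
|---|---|---|---|
| no | no | not allowed | not allowed |
| no | yes | not allowed | may be allowed |
| yes | no | not allowed | may be allowed |
| yes | yes | may be allowed | may be allowed |

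The rules disagree in rows 2 and 3, which is 2 of 4 combinations.

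*Row 3 (low exposure, tolerability not shown).* The safety assessment that Section 5.1 requires before each escalation largely blocks this case, whatever 7.1.2 says.

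*Row 2 (exposure as expected, limit dose tolerated).* The safety assessment does not block this case, because tolerability is what it looks for. In the terms of Table 10, a tolerated top dose would typically be an E, and 7.2.2 says that E at the highest level means staying. So 5.5.2.2 and 7.2.2 both point against escalating, and 7.1.2 is the outlier. This row is the practical gap.

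*Does 7.2.2 resolve it?* Not fully. Read literally, it would also forbid row 4, which 5.5.2.2 allows. It is a conservative default and does not say which condition opens a dose above the limit.

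**The ATD stagger.** Take the first participant's first dose as Day 1 and find the earliest start for the third:

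- Section 7.2.1 read alone: first doses on Days 1, 8 and 8. Participant-days observed before the third: (8 − 1) + (8 − 8) = 7.
- Section 5.1: first doses on Days 1, 8 and 15. Participant-days observed before the third: (15 − 1) + (15 − 8) = 21.

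Section 5.1 attaches its interval to the three-participant allowance itself, so the two sections read together give Day 15. The Day 8 result arises only if a site consults 7.2.1 and not 5.1.

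**The case against.** The strongest reply on the dose limit is that nobody can act on 7.1.2 alone. The permission is discretionary. Sites cannot open a dose level, because the sponsor does so through IWRS after a consensus review that includes PK/PD data. When the subcutaneous maximum was last raised, Section 5.5.2.2 records that this was done by protocol amendment (06), on a composite evaluation that included PK. Section 7.2.2 supplies a conservative default. All of this stands, and it limits the practical effect. It does not remove the conflict: a consensus review still needs one criterion to apply, and the protocol offers two.

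Three stronger readings are tempting, and the documents do not support them.

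- A reader might take 2 of 4 as a measure of how often the rules would diverge. It counts combinations and is not a frequency. One of the two is largely blocked already.
- A reader might argue from the intratumoral cap in Section 5.5.2.1 ("the proposed maximum dose/exposure for the trial is a dose of or an exposure limit of whichever is lower") and from the freedom to dose above the intratumoral MAD that Arm 4 has lost its exposure control. Those passages are context only. The loss of the exposure condition follows from the word *or* in 7.1.2, and only when 7.1.2 is followed in place of 5.5.2.2.
- A reader might call the two stagger texts contradictory. They are not: 7.2.1 is silent on the third participant, and following 5.1 satisfies both.

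**Conclusion.** The mismatch over the Arm 4 limit is real and should be corrected. Section 7.1.2 as written permits escalation on tolerability alone with exposure as expected, which 5.5.2.2 forbids and which also sits against 7.2.2.

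Its size is one practically relevant combination of conditions. How often it would occur cannot be estimated, because the limit and exposure values are redacted. It matters only if Arm 4 reaches the limit without finding an MTD. Section 5.5.2.2 describes Arm 4 escalation as ongoing with acceptable safety, but the documents do not show how close it is to the limit, and nothing in them shows that a dose has been or will be raised on the looser rule. The conclusion assumes that 5.5.2.2, which sets out the rationale for the maximum, carries the intended rule.

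The stagger is a harmonisation point only. Arm 4 opened after an Arm 1 level had completed evaluation under mTPI (Synopsis), so Arm 1 has left ATD. Any remaining relevance is to ATD cohorts in Arms 2 or 3, whose status is not stated.

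**What to change.** 1. In Section 7.1.2, replace *, or if* with *and*, so that both conditions are required as in 5.5.2.2.
2. In Section 7.2.2, note that in Arm 4 an E at the highest dose level means staying unless both conditions of 5.5.2.2 are met.
3. As an editorial change, make the 7-day interval in Section 7.2.1 apply to the first 3 participants, each first dose at least 7 days after the previous one, to match Section 5.1.

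If the sponsor does intend tolerability alone to suffice, that rule should be stated identically in 5.5.2.2 and 7.1.2.

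The cost is three wording changes in an amendment and a memo to sites, with no effect on sample size. The real downside is less freedom to exceed the subcutaneous limit when exposure is as expected, which 5.5.2.2 already withholds. The stagger edit adds no delay for a site already following 5.1. For a site working from 7.2.1 alone, a third ATD participant could start up to 15 − 8 = 7 days later.
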